2.1 What is your research question?  State hypothesis or primary objective, and provide a brief background on subject population, treatment procedures, and the rationale for conducting the study.  This study aims to test whether there is a difference in the analgesic effect between TAP blocks and surgical infiltration during the first 72 hours following laparoscopic and robotic total hysterectomies.  Laparoscopic and Robotic assisted hysterectomy is a surgical procedure that is a minimally invasive way in which to remove the uterus, which has less scarring and fewer complications. However, this procedure, much like its open-surgical counterpart, is often associated with significant post-operative pain. To augment this pain there are many

different analgesic techniques available to offset pain. Ultrasound-guided transversus abdominis plane (TAP) block is one such procedure involving the injection of a local anesthetic into the plane of the transversus abdominal muscle where the terminal branches of nerves lie. A similar, yet different analgesic approach is that of direct injection of local anesthetic into the incision by the surgeon during or just after surgical procedures. These two approaches have both been proven to decrease post-operative pain in patients for many procedures, but never compared to one another.

#### Background and Significance

Even with the advancement of using laparoscopic and robotic technologies in total hysterectomies, patients still suffer from pain. This study hopes to use a randomized controlled double-blinded approach to investigate the different analgesic outcomes from surgical infiltration of analgesics to that of ultrasound-guided transversus abdominis plane (TAP) blocks in this procedure.

Other studies have looked at the enhanced analgesic efficacy of both TAP blocks in laparoscopic and robotic procedures, as well as that of direct infiltration of anesthetics into the incisions following surgery. Up to this point, however, these two practices have not been undertaken in a single double-blind study in which to compare the analgesic efficacies.

#### 2.2 Who developed the research plan/protocol?

Principal Investigator     Business and Industry Sponsor     Other:

#### 2.3 Explain how the study design and methods will answer the research question.

This is a double blinded randomized study. All patients will receive one form of local anesthetic pain relief either from TAP or infiltration. Patients will be randomized to one of two study arms in a double-blinded, placebo controlled study. All patients will receive a TAP infiltration and all patients will receive infiltration into the incision. In one arm the TAP infiltration will contain 10 mL of 0.25 % bupivacaine with epinephrine injected followed by 20 mL of a 50:50 mixture of liposomal bupivacaine and normal saline. This will then be repeated on the contralateral side. In the same arm the surgeon infiltration into the incision will consist of 10 ml of normal saline per port site, 5 ml prior to incision and 5 ml prior to closure at each port site.

In the second arm the bilateral TAP infiltration will consist of 30 mL of normal saline per side. In the same arm the surgeon infiltration will consist of 10 mL of 0.25% bupivacaine per port site. The surgeon infiltration will consist of 5 ml of 0.25% bupivacaine prior to incision and 5 ml of 0.25% bupivacaine prior to closure at each port site.

A TAP infiltration is an injection of local anesthetic under the covering of the transversus abdominis muscle layer which provides effective post operative analgesia. This layer is found using an ultrasound, which is a beam of high frequency sound that allows one to visualize images in the body. Then using this ultrasound we can see our needle as it pierces the covering of the transversus abdominis muscle layer and watch as the local anesthetic is infiltrated into this plane. This is done on both sides of the abdomen to provide analgesia to the skin, muscle, and facial layers of the abdomen. This is currently standard of care at our institution and will be performed within one hour of surgical incision. The injection will consist of 10 mL of 0.25% bupivacaine with epinephrine followed by 20 mL of liposomal bupivacaine saline mixture or 10 ml of saline followed by 20 ml of saline and then repeated on the contralateral side.

Surgical Infiltration of the study solution will be performed both prior to incision and at the end of surgery just prior to closure of incisions. At each time, the surgeon will inject 5 mL of 0.25% bupivacaine into each of the port site

incisions.

Investigational Drug Service (IDS) pharmacy will be charged with the blinding of medications vs. saline for these procedures.

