**2.4 What will the subjects be asked to do solely for the purpose of this research?**

Subjects will be asked to be randomly assigned to receive either a TAP with liposomal bupivacaine or infiltration with bupivacaine. They will also be asked to answer questions at various time points related to their pain, answer a survey on their quality of recovery. They will also be asked to allow the research staff to access their medical chart to obtain information about their pain medication use, complications, demographics, and time of discharge.

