### Section 3 [Risks and Benefits](#)

**3.1 Please indicate if the proposed research will include any of the following (check all that apply). The list below is not exhaustive but represents common elements or procedures in research with associated risks that are frequently overlooked or not clearly articulated.**

- |   |
|---|
|  Administration of physical stimuli                                     |
|  Probing for personal or sensitive information in surveys or interviews |
|  Collection of data with identifiers                                    |

	Possible invasion of privacy of the subject or the subject's family
	Modification or extension of a surgical process to achieve research related objectives.
	Major changes in diet, exercise, or sleep
	Manipulation of psychological or social variables such as sensory deprivation, social isolation, psychological stresses
	Placebo Use
	Treatment will be withheld or subjects will discontinue current treatment (a wash out period is included)
	None of the above

**3.2 Describe in detail the nature and degree of the risk associated with participation.** The risks must be disclosed in the consent form. Include in the response all potential risks, not just those indicated in the checklist above.

There is the potential of loss of privacy as the medical chart is accessed by the research staff. In addition there is a placebo used however no patient will be without pain medication. The TAP will either consist of local anesthetic or saline. When the TAP consists of saline the infiltration will consist of local anesthetic and when the TAP consists of local anesthetic the infiltration will consist of saline.

With injection of local anesthetic there is risk of the block or infiltration not working. There is risk of it being injected in the wrong area and there is risk of local anesthetic toxicity albeit the dosages used are well below those which would place the patient at risk of local anesthetic toxicity.

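### Section 2.3 of the protocol ends by giving bupivacaine at every port site in every patient, contradicting its own saline port infiltration for the active-TAP arm

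*Protocol*

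**What the plan says.** Section 2.3 of the protocol first sets out a double-dummy design in which every patient has both a TAP injection and port-site infiltration. It states the principle that "All patients will receive one form of local anesthetic pain relief either from TAP or infiltration". For the arm with local anesthetic in the TAP it says "In the same arm the surgeon infiltration into the incision will consist of 10 ml of normal saline per port site", split as 5 mL before incision and 5 mL before closure. The other arm has saline in the TAP and 10 mL of 0.25% bupivacaine per port, split in the same way.

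Two procedural paragraphs follow. The one on the TAP gives both possible contents, ending with the "liposomal bupivacaine saline mixture or 10 ml of saline followed by 20 ml of saline". The one on infiltration opens neutrally, "Surgical Infiltration of the study solution will be performed both prior to incision and at the end of surgery", and then says "At each time, the surgeon will inject 5 mL of 0.25% bupivacaine into each of the port site" incisions. The section closes by assigning the blinding: "Investigational Drug Service (IDS) pharmacy will be charged with the blinding of medications vs. saline for these procedures".

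Section 2.4 describes assignment to "either a TAP with liposomal bupivacaine or infiltration with bupivacaine". Section 3.2 states the pairing rule: "when the TAP consists of local anesthetic the infiltration will consist of saline".

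**The concern.** The closing infiltration paragraph applies to all patients as written. In the saline-TAP arm it agrees with the arm definition. In the active-TAP arm it does not: the definition puts saline at the ports and the paragraph puts bupivacaine there. It also conflicts with the principle of one active site per patient and with sections 2.4 and 3.2.

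The sentence tells the surgeon what to inject and when, so it is working text and not background. If it were carried into pharmacy or operating-room instructions, two things would follow:

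- The port placebo would disappear, and the comparison would become TAP plus infiltration against infiltration alone. The research question in section 2.1 is TAP against infiltration.
- The assurance in section 3.2 about dosages and local anesthetic toxicity, given alongside the one-active-site pairing, would not describe what the active-TAP arm received.

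Both consequences depend on the sentence being followed literally.

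**Working it through.** **Is it the same injection?** Yes. All three descriptions give 5 mL before incision and 5 mL before closure at each port, and 5 mL × 2 = 10 mL per port. Volume and timing agree, so the conflict concerns content only.

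**Content of the port injection, by source:**

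| Source | Active-TAP arm | Saline-TAP arm |
|---|---|---|
| Section 2.3, arm definitions | Saline | 0.25% bupivacaine |
| Section 2.3, last infiltration paragraph | 0.25% bupivacaine | 0.25% bupivacaine |
| Section 2.4, assignment | Active agent named for the TAP only | Bupivacaine |
| Section 3.2, pairing rule | Saline | Local anesthetic |

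The disagreement is confined to the active-TAP column, and only the last infiltration paragraph is out of line.

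**Is the sentence just shorthand?** The TAP paragraph directly above it serves the same purpose and spells out both the active and the saline content. The infiltration paragraph lacks the second half. The neutral opening does not settle the matter, because a reader could take the next sentence as defining the solution.

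**Size if followed literally in the active-TAP arm:**

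- Strength: 0.25% = 2.5 mg/mL.
- Per port: 10 mL × 2.5 mg/mL = 25 mg, where the arm definition gives 0 mg.
- The number of ports is not stated. Assuming 3, 4, 5 or 6 ports gives 30, 40, 50 or 60 mL, that is 75, 100, 125 or 150 mg.
- Planned TAP content in that arm: 2 sides × 10 mL × 2.5 mg/mL = 50 mg of 0.25% bupivacaine, plus 2 sides × 20 mL × 0.5 = 20 mL of liposomal bupivacaine.
- The liposomal strength is not stated, so a total in mg and a relative increase cannot be calculated from the protocol.

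No sample-size, power or error-rate figure enters this point.

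**The case against.** The best case on the other side is that the protocol largely resolves the conflict itself. Both arms are defined explicitly, sections 2.4 and 3.2 repeat the either/or design, and the paragraph at fault opens by referring to the study solution. The next sentence gives the pharmacy the blinding of drug against saline for both procedures, which makes sense only if saline is a possible port content. Under pharmacy blinding, the arm definitions and not a technique paragraph would naturally determine what is in the syringe. Nothing in the protocol shows the sentence being carried into working instructions, which are not available for review. On this view it is an editorial slip, and the milligram range stacks an assumed port number on an unlikely reading.

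Much of this stands. The intended design can be recovered, the consequences are hypothetical, and no toxicity threshold, body weight or liposomal strength is given, so the section 3.2 assurance has not been shown to fail. It does not remove the conflict. The pharmacy sentence assigns the blinding without restating the content of each arm, so section 2.3 remains the fullest statement of what each arm receives at each site, and it gives two contents for one blinded injection.

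**Conclusion.** The point holds. Section 2.3 contradicts itself, and section 3.2, on what the active-TAP arm receives at the port sites. This is probably a drafting omission, but it concerns the content of a study injection and should be corrected.

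Followed literally, the text would give that arm 25 mg of bupivacaine per port where its definition gives saline, or 75 to 150 mg over an assumed 3 to 6 ports, and would change the treatment contrast. If the arm definitions are followed, neither effect arises. No claim is made about a toxic dose or about the relative increase in exposure.

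**What to change.** Reconcile the last infiltration paragraph of section 2.3 with the arm definitions in that section and with section 3.2, so that a single description governs each arm. Two forms of wording would do this: refer only to the blinded solution supplied by pharmacy, or state the content arm by arm as the TAP paragraph does. Then check that the pharmacy and operating-room instructions match, and that the dosage statement in section 3.2 refers to the reconciled content. Which content is correct is for the investigators to state.

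The cost is a one-sentence protocol correction and a check of the working instructions.

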**2.4 What will the subjects be asked to do solely for the purpose of this research?**

Subjects will be asked to be randomly assigned to receive either a TAP with liposomal bupivacaine or infiltration with bupivacaine. They will also be asked to answer questions at various time points related to their pain, answer a survey on their quality of recovery. They will also be asked to allow the research staff to access their medical chart to obtain information about their pain medication use, complications, demographics, and time of discharge.

**2.5 Does the study involve treatment?**

- No.
- Yes. List any procedure that would be performed if research was not conducted (i.e. procedures performed for diagnostic or treatment purposes).**

all procedures would be performed if research was not conducted as both the TAP and infiltration are standard of care.

**2.6 Indicate whether your research includes any of the following to determine which supplemental forms must be submitted with your application:**

If the research includes	Appendices and supplemental materials required
 Administration of approved or unapproved drugs, chemical or biological agents	Appendix E required with the application
 Administration of approved or unapproved devices	Appendix F required with the application
 Genetic testing (whether or not results are returned to subjects)	Appendix G required with the application
 Use of (collecting or having access to) Protected Health Information (PHI)	Appendix H required with the application
 Field Work	Appendix L required with the application
 Use of a deceptive technique	Appendix N required with the application A debriefing script is also required.
 Community based participatory research	Appendix Q required with the application
 Collection or storage of biological samples	Appendix T required with the application

(including blood draws, marrow biopsy sampling, biopsy of other tissues)	
 Use of Magnetic Resonance devices housed at the Center for Magnetic Resonance Research (CMRR)	Documentation of CMRR Safety Committee approval required.  CMRR users must submit the completed CMRR Device and Safety Review form to the CMRR prior to submission of their IRB application. A draft copy of the IRB application must be included for CMRR Safety Committee review. Documentation of approval by the CMRR Safety Committee will be provided to the researcher to include with the IRB application.
 Potential biohazards including recombinant and synthetic nucleic acid, human gene transfer, biologically-derived toxins or infectious agents	Institutional Biosafety Committee approval required prior to final approval. If an IBC application has been submitted for this research, provide the study number.
 Biologically-derived toxins (including truncated or mutated toxins)	Institutional Biosafety Committee approval required prior to final approval. If an IBC application has been submitted for this research, provide the study number.
 Infectious agents (bacteria, viruses, protozoans, fungi)	Institutional Biosafety Committee approval required prior to final approval. If an IBC application has been submitted for this research, provide the study number.
 Use of radiation (x-ray imaging, radiopharmaceuticals, external beam or brachytherapy)	All University Radiation Protection Committee (AURPAC) approval required prior to final IRB approval.

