**3.3 Describe the precautions that will be taken to minimize each of the risks identified in questions 3.1 and 3.2.**

All patient charts will be accessed by a trained research personnel. They will not record any identifiers. Patient's will be asked if they are willing to answer questions prior to each round of questions regarding pain scores and surveys.

All TAP and infiltration are standard of care. Either or would be used if we were not doing the research. The TAP infiltration is performed by trained anesthesiologists and are under ultrasound real time guidance. The infiltration is performed by trained surgeons.

**3.4 List any anticipated direct and societal benefits to participation in this research project.** If none, state that in the space provided below and in the consent form. The benefit of receiving treatment is not necessarily a benefit to participation in the research project. ***Compensation paid to subjects is not considered a benefit.***

none

**3.5 Justify the risk in terms of the potential scientific yield and in relation to the anticipated benefits to the subjects.**

The benefits of this study would be to find the most effective method of pain control which would not only decrease patient's pain but decrease their use of opioids. As opioids are a significant burden on society in terms of misuse, addiction, and even death. It is important we find ways to minimize postoperative pain and postoperative

opioid use.

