**12.3.2 Will subjects or a third party be charged for research related procedures?**

No

Yes      **Explain:** These are standard of care and as such are charged to the patient as per routine  

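### Section 2.5 counts every study procedure as usual care, yet the double-dummy design adds one research-only saline procedure per patient that 2.4, 3.2 and 12.3.2 do not account for

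*Protocol*

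**What the plan says.** Section 2.5 of the Protocol asks which procedures would take place without the research. The answer is that "all procedures would be performed if research was not conducted as both the TAP and infiltration are standard of care".

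Section 2.3 sets out what each patient receives: "All patients will receive a TAP infiltration and all patients will receive infiltration into the incision". Only one of the two is active: "All patients will receive one form of local anesthetic pain relief either from TAP or infiltration". In the arm with the active TAP, "In the same arm the surgeon infiltration into the incision will consist of 10 ml of normal saline per port site", given as 5 mL before incision and 5 mL before closure. In the other arm, "In the second arm the bilateral TAP infiltration will consist of 30 mL of normal saline per side".

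Section 3.3 describes care outside the study differently from 2.5: "Either or would be used if we were not doing the research".

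Three other sections bear on the same point:

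- Section 2.4, on what is asked of patients for research purposes alone, lists random assignment to an active TAP or an active infiltration, pain questions, a recovery survey and chart access.
- Section 3.2 names both saline combinations. It opens its account of injection risk with "With injection of local anesthetic there is risk of the block or infiltration not working", then adds injection in the wrong area and local anesthetic toxicity.
- Section 12.3.2, on charges for research-related procedures, explains: "These are standard of care and as such are charged to the patient as per routine".

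**The concern.** Sections 2.4, 2.5 and 3.2 are where the application separates what the study adds from what the patient would have had anyway. A double-dummy design always adds something, because each patient needs an inert version of the technique she was not assigned. If 2.5 classes everything as usual care, that added procedure has no place in the document as a research intervention.

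What is at stake is patient protection, not the analysis. The saline TAP is a bilateral ultrasound-guided needle procedure in the abdominal wall with no analgesic content. The saline port injections are repeated at every port for the same blinding purpose. A procedure done only for research should be identified as such, have its own risks stated, and have a stated payer. As written, the standard-of-care premise in 2.5 carries over into sections where it does not fit the saline procedure.

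**Working it through.** The plan states no figure on this point, so the check is a comparison of sections and a count.

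**Step 1. Procedures delivered per patient (2.3).** TAP injection plus port-site infiltration = 2, in both arms. One is active and one is saline.

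**Step 2. Procedures per patient without the research (3.3).** One technique or the other = 1.

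**Step 3. Difference.** 2 − 1 = 1 research-only procedure per patient. With 60 patients to be enrolled (4.2), that is 60 × 1 = 60 research-only procedures, so 60 of 60 patients are affected.

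**Step 4. What that procedure is.**

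| Arm | Active procedure | Research-only procedure |
|---|---|---|
| TAP | Bilateral TAP | Saline at each port: 5 mL + 5 mL = 10 mL per port |
| Infiltration | Port-site bupivacaine | Bilateral saline TAP: 2 × 30 mL = 60 mL |

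Section 2.3 gives no number of ports, so a total port volume cannot be computed from the document, and the point does not need one. The passages relied on here give no allocation ratio. If it is 1:1, about 60 / 2 = 30 patients would receive each type of saline procedure.

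**Step 5. Does the result depend on how 3.3 is read?** Its sentence is loosely worded. Suppose usual care sometimes combined both techniques. Both would then be given with local anesthetic, for pain relief. Nothing in the Protocol describes a saline TAP or saline infiltration as usual care, and 2.3 presents the TAP as standard of care because of its analgesic effect. So 2.5 is inaccurate for the saline procedure on either reading. Section 3.3 shows in addition that the number of procedures rises.

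**Step 6. Follow the premise through the other sections.**

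- 2.4: neither saline procedure appears in the list of research-only activities.
- 3.2: placebo use is acknowledged, with the assurance that no patient goes without pain medication. The three injection risks given (failure, wrong area, toxicity) are introduced as risks of injecting local anesthetic. No procedural risk is stated for a saline injection.
- 12.3.2: the explanation describes the charged procedures as standard of care and neither includes nor excludes the saline procedure.

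No weight is placed on boxes that appear unticked in the form, since tick marks did not survive reliably in the text available for review.

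**The case against.** The strongest reply is that the placebo is openly disclosed. Section 3.1 ticks placebo use, 3.2 sets out both saline combinations, and 2.3 describes the double-dummy design in full. An ethics committee reading the whole application would see that every patient has a saline procedure. This stands. A reader might infer that the sham injections were concealed, or that the committee's risk judgement turned on the sentence in 2.5; the document supports neither. The gap is narrower: research-only status and procedural risk are not stated.

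Second, the thin account of needle risk is not peculiar to saline. Section 3.2 says little about needle or tissue injury for the active TAP either, and the precautions in 3.3 (trained operators, real-time ultrasound guidance) apply whatever is in the syringe. This also stands. It means the risk text should cover the injections generally, including when saline is used. It does not answer the point that a saline injection currently has no stated procedural risk.

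Third, a reader might infer from 12.3.2 that patients will be billed for a placebo. The document does not establish that. The word at the start of its explanation has no clear referent and may mean only the active procedures. The yes/no mark is not legible in the text available, the form refers in 12.3.3 to a separate billing grid that is not shown, and Section 10 names departmental anesthesiology funds. What remains is that 12.3.2 leaves the question open.

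Fourth, the consent form is not available, so whether it describes the saline injections and their risks cannot be judged. No finding is made about it.

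Last, this is inconsistent wording between sections, not a flaw in the design. That is correct: the double-dummy structure is not faulted.

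**Conclusion.** The concern holds in a limited form. Section 2.5 is wrong as written: it conflicts with 2.3 on what is delivered and with 3.3 on what usual care would be. The extent is one research-only saline procedure in every patient. This rests only on 2.3, 3.3 and the planned enrollment; the 1:1 split is an assumption used solely for the approximate count per arm.

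Confidence differs by part. The conflict between 2.5 and 2.3/3.3, and the omission from 2.4, are certain from the text. The missing procedural risk in 3.2 is also plain, with the qualification that the description is thin for active injections too. For 12.3.2 the finding is ambiguity only. Randomization, blinding, endpoints and statistical inference are untouched. The point is worth correcting because it concerns what patients are exposed to for research purposes and the remedy is cheap.

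**What to change.** Bring 2.4, 2.5, 3.2, 3.3 and 12.3.2 into line with 2.3:

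- **2.4 and 2.5:** name the saline TAP and the saline port-site injections as done only for the research, and limit the standard-of-care statement to the active procedures.
- **3.2:** state the needle and procedural risks of the injections, making clear that they apply when saline is used, and check that the consent form says the same.
- **3.3:** keep the description of usual care consistent with the revised 2.5, and say that the saline procedure is additional.
- **12.3.2:** state whether the saline procedure is among the charged items and who pays for it, so that it is not charged as standard of care by default.

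The cost is wording changes in the Protocol, any matching change to the consent form, and possibly a charge borne by study funds. Design, sample size and staffing stay as they are.
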